Study Protocol and Statistical Analysis Plan

Project Title:

Version Date:

Transitional rehabilitation in CABG patients

4-17-17

NCT number:

NCT03892460

**Principal
Investigator:**

[name]

Co-Investigator:

[name]

Grant Sponsor:

University of Vermont, College of Medicine, Department of Medicine

Summary:

Coronary artery bypass graft (CABG) surgery is a common surgical procedures and an important treatment option for coronary artery disease. As with any major surgical or medical procedure, the period of rest and recovery that follows is associated with cardiorespiratory and skeletal muscle deconditioning that can leave patients feeling weak and fatigued. Cardiac rehabilitation exercise training is recommended to recover lost strength and fitness. However, patients typically do not begin cardiac rehabilitation until 4-6 weeks following CABG surgery. Rehabilitative interventions to bridge the period between discharge following CABG surgery and the start of cardiac rehabilitation could improve patient cardiorespiratory and their ability to perform daily activities.

The goal of this research study is to understand whether an at-home exercise program started soon after CABG surgery, and continuing for 4 weeks following discharge from the hospital, can serve as a bridge between surgery and the start of cardiac rehabilitation to preserve physical function. Volunteers will be randomly assigned to receive neuromuscular electrical stimulation (NMES) of their quadriceps muscles or not to receive NMES (control group). Volunteers will be evaluated prior to CABG (Pre-surgery testing), upon discharge and 4 weeks Post-CABG surgery. Assessments will include measurements of physical function by the Short Physical Performance Battery and 6 min walk tests, as well as assessment of subjective physical functional capacity and quality of life using the Medical Outcomes Short form 36. Additionally, accelerometry will be used to monitor weight-bearing physical activity during the 4 week treatment phase.

If successful, results from these studies will advance knowledge by providing proof-of-principle evidence for the utility of NMES to counter physical functional deterioration in the early, post-surgical period following CABG. Additionally, our findings may advance postoperative care of CABG patients by providing a clinical intervention to bridge a gap in rehabilitation services prior to entry into formal CR. Maintaining functional capacity in patients post-discharge may reduce the risk for re-hospitalization and progression towards disability. Greater functionality upon entry into CR may permit greater functional and health benefits from exercise during CR.

Purpose:

CR programs were initially developed to counter the deconditioning effects of medical and surgical interventions in cardiac patients and they have well-accepted health and survival benefits (1). Although CR is an important part of the care continuum (2), CABG patients typically do not start CR until ~4-6 wks after discharge (3). During this period, patients can experience further deterioration in physiological reserve, with increased risk for post-operative complications, readmission and development of physical disability (4-6). Whereas a large number of studies have focused on transitional care initiatives in medical and surgical cardiac populations to improve clinical outcomes and minimize costs (7), very few have focused on bridging this gap in physical rehabilitation care.

One reason for the absence of transitional rehabilitative care services in cardiac surgical patients is the inherent difficulty of intervening in a post-surgical population, as pain and limited mobility from surgical wounds diminishes motivation towards classical exercise. Moreover, reduced physical function related to surgery and hospitalization may render patients unable to perform basic activities of daily living at home, much less exercise. These hurdles represent a significant barrier to bridging the gap in rehabilitative care of cardiac surgical patients. Alternative exercise modalities that confer a training effect, but that do not have the physical requirements of classical aerobic or resistance training, could bridge this gap. Optimal candidates should induce an exercise training response, integrate easily into outpatient and home environments and be easy to use and inexpensive.

NMES is an intervention that fulfills many of these criteria. An inexpensive (~\$500), FDA-approved, portable, hand-held NMES unit permits non-volitional initiation of muscle contractions that can mimic resistance- or aerobic-type exercise (8), producing a training response that is near comparable to classical aerobic training (9, 10). NMES improves muscle size, strength and performance in older adults with chronic disease (11), and counteracts muscle atrophy coincident with pathophysiologic catabolic stimuli (12-14) and muscle disuse (15), both of which occur in the post-operative period following CABG. Although NMES has been studied in stable heart failure patients (16), to our knowledge, it has never been employed in CABG or other cardiac surgical populations as a potential bridge therapy from post-

operative discharge to the start of CR.

Transitional care following hospitalization has been recognized as a national priority (17, 18) and efforts to implement new services were incentivized by the Affordable Care Act (19). Numerous studies have shown the utility of transitional care services to improve outcomes, reduce unnecessary use of health services and decrease costs (20, 21), but few of these studies have focused on ways to extend rehabilitation services (22) and fewer still have focused on these services following CABG surgery.

CR is an important part of the rehabilitative care of cardiac medical and surgical patients that restores physiological reserve lost during the acute disease event and subsequent hospitalization and convalescence, as well as conferring long-term health benefits (23). Although this deterioration in physiological reserve is well-accepted, our current knowledge of such adaptations in CABG patients is limited and there are currently no evidence-based interventions that bridge rehabilitative care between discharge and the start of CR, aside from acute, in-patient rehabilitation facilities in cases of substantial frailty. Successful completion of our studies would impact the field of transitional care of CABG patients in several ways:

Fill an important knowledge gap. Our results will provide the first characterization of early, post-surgical functional and physiological adaptations to CABG (in patients randomized to control). Studies have noted that CABG patients have reduced self-reported or objectively-measured physical function post-surgery compared to non-surgically-treated patients. However, no study has systematically tracked the erosion of physical functional capacity from CABG surgery to the start of CR. Knowledge of the extent of the reduction in functional capacity due to CABG can spur the development of new transitional care services aimed at improving outcomes/costs.

Define the utility of NMES to prevent early, post-surgical erosion in physiological capacity. Based on studies in other post-surgical populations, we anticipate uncovering novel effects of NMES to prevent the loss of physiological function, providing an important evidence base upon which to build support for further studies evaluating the utility of NMES in CABG recipients. Maintenance of physiological function in the post-CABG period may improve the response to CR, particularly in those with low baseline functionality (24). Because NMES is FDA-approved, inexpensive, portable to the outpatient and home environments and there are clinicians already trained in its use (PTs/OTs), barriers to its broader clinical application to the CABG population are minimal.

Relevance to other surgical populations. Demonstration of the utility of NMES in the post-surgical CABG population has direct relevance to other older adult surgical populations beyond cardiac populations, where follow-up rehabilitative care, such as CR, is not available, as well as other non-surgical populations (eg, heart failure, COPD patients). NMES may serve as an inexpensive, transitional care service that allows these patients to maintain/regain functional reserve.

References.

1. [name], P. A. (2001) Cardiac rehabilitation and secondary prevention of coronary heart disease. *N Engl J Med* **345**, 892-902
2. Balady, G. J., Williams, M. A., [name], P. A., Bittner, V., Comoss, P., Foody, J. M., Franklin, B., Sanderson, B., and Southard, D. (2007) Core components of cardiac rehabilitation/secondary prevention programs: 2007 update. *Circulation* **115**, 2675-2682

The goal of this application is to explore the utility of neuromuscular electrical stimulation (NMES) to counter the early, post-surgical deterioration in physical functional capacity. We chose NMES because it permits non-volitional initiation of muscle contractions that can produce an exercise training response similar to classical exercise training, with near comparable effects. We will test the ability of NMES to preserve physical function, as measured by the Short Physical Performance Battery (SPPB), a metric whose change in the first month post-hospitalization has been shown to predict re-hospitalization and death and that is validated for use in physically compromised elderly populations. We will also assess 6-minute walk (6MW) performance as a secondary outcome, a metric that is commonly used for FDA approval of various interventions that seek to improve physical function/fitness. Our rationale for the proposed studies is that interventions directed towards preventing deleterious skeletal muscle changes during this period and maintaining functional capacity will enhance the effects of CR to improve functionality and future cardiovascular risk. We will accomplish these goals using a randomized, controlled design. Based on our preliminary data, we hypothesize that NMES will prevent deleterious reductions in physical function by preserving skeletal muscle size function. To address this hypothesis, we propose a single aim:

Aim: Define the utility of NMES to preserve or increase physical functional capacity in patients during the period following CABG and prior to entry into CR.

Primary Clinical Outcome: NMES will diminish CABG-induced erosion of physical functional capacity, as assessed by the SPPB.

Secondary Clinical Outcome: NMES will diminish CABG-induced erosion of physical functional capacity, as assessed by the 6MW.

METHODS AND PROCEDURES

Study Design:

We will use a prospective design, in which patients scheduled for elective CABG will be recruited and evaluated prior to CABG (Pre-surgery) and upon discharge (Discharge) for physical function (SPPB Testing and 6 min walk). Patients will be recruited for this study during the normal process of clinical recruitment for cardiac rehabilitation. This includes patients from cardiothoracic consultation lists and/or those scheduled for elective CABG. In some instances, we will identify patients from cardiothoracic consultation lists who are or will be scheduled for CABG, but are not on the surgical unit. We will contact these patients by phone regarding participation in cardiac rehabilitation and, at that time, introduce this research study. Patients will be randomized (1:1) to NMES or control intervention (n=18/group; Treatment Phase), with stratification for age and sex. Following completion of the 4 wk intervention,

volunteers will undergo Post- Testing, which will be identical to Pre-surgery and Discharge testing. Each protocol phase is described below.

Pre-surgery testing Baseline testing will occur prior to CABG surgery and at discharge and consist of functional assessment by the SPPB and a quality of life (QOL) questionnaire (MOS-SF36). Tests are described below.

Discharge testing will repeat Pre-surgery testing and include a 6MW. At this time, volunteers will receive an accelerometer, which will be worn during three (3) 5-day periods during the Treatment phase.

Treatment Phase

Patients will be randomized (1:1) to NMES or control intervention and will continue in this Treatment phase until 4 weeks post-CABG surgery.

4 wk Post-surgery testing will be identical to Discharge testing.

Procedures:

All of the procedures and interventions on volunteers recruited for these studies are carried out solely for research purposes, as none are part of standard therapy in CABG patients.

Physiological Testing (during Pre-surgery (excluding 6 MW), Discharge and 4 wk Post-surgery testing)

SPPB will be measured, as described by us (1), as this assessment is prognostic for functional competence and mortality in cardiac surgical patients (2). This measure takes ~5 min to perform and is comprised of: 5 repeated chair stands, balance testing (3 tasks each 10 s long) and a 4 meter walk. As increasing SPPB score in the first month post-discharge in a sample of elderly patients with diverse clinical backgrounds was associated with lower risk for rehospitalization and death (3), improvements in, or maintenance of, this metric would provide strong evidence for the clinical utility of NMES. We have experience with this measure in cardiac populations (4).

6 MW was developed to assess cardiopulmonary fitness in patients with lung and cardiac disease (5), but has been used widely to assess disability in older adults (6) and is the most common metric used when seeking FDA approval for interventions to improve physical function. We have experience with this measure in heart failure patients (7).

Medical outcome survey short form 36 is a commonly used questionnaire to assess subjective quality of life and physical function.

Accelerometry (Lifecorder Plus) will be used to monitor steps taken, caloric cost and minutes in activity and will be performed for three (3) 5-day periods during the Treatment phase of the study.

Treatment phase

NMES will be carried out bilaterally on the quadriceps using a portable stimulator (EMPI Continuum). Two adhesive electrodes will be affixed to the anterior surface of each thigh: ~1 cm distal to the inguinal crease and ~5 cm proximal to the patella, just lateral to the midline of the thigh to assure that it does not interfere with incisions for vein harvest. Symmetrical, biphasic pulses (400 μ s duration at 25 Hz) will be used, with a duty cycle of 25% (10 s on, 30 s off). Patients will be trained to conduct NMES sessions and will select stimulation intensities sufficient to cause visible muscle contractions below their pain threshold. Training in the use of the NMES device will begin within 96 hrs of transfer to the surgical step down unit. This training will consist of one session per day of ~15 min to familiarize the volunteer with the unit and the exercise/contraction stimulus. Upon discharge, NMES sessions will occur 5 d/wk once per day for 45 min per occasion (5 min low-intensity warm-up, 40 min higher-intensity stimulation) for 4 wks. This program is meant to mimic an aerobic-type exercise stimulus (8) and has been shown in heart failure patients to have functional benefits over a similar treatment period (9, 10). The 4 wk duration reflects the approximate average time that most CABG patients take to enter CR at our center. We acknowledge that the NMES training load is substantial, but have modeled this program on others that have shown morphological and functional effects in heart failure patients (11). At this exploratory stage, we feel that it is essential to use a stimulus that affects muscle size and function, with future studies modifying the NMES dose to establish a threshold that elicits a training effect with the highest subject

compliance rate. Daily logs and weekly phone contacts will be used to track compliance, and compliance will be covertly monitored using the device software.

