An individual research record will be kept on each volunteer in compliance with HIPAA standards. This record will contain identifying data, demographic information and results from all clinical research measurements and evaluations. The results of all testing will be kept confidential. All materials gathered in conjunction with the proposed studies will be used for research purposes only and will be available only to research personnel working on these studies, who have obtained proper training in human subjects research and privacy protection.

Statistical Analysis Plan:

Our primary goal is to assess changes in SPPB score and 6 MW between study groups to test whether NMES prevents the erosion of functionality from admission to 4 wk post-discharge (approximate time for starting CR). A general linear mixed model will be used, with group and time as fixed effects. The primary comparison will be between measures at admission and 4 wks post-discharge, as changes over this time period will reflect the effects of the surgery, post-op recovery and post-discharge/pre-CR periods. Because function may be impaired pre-surgery due to angina/dyspnea/etc, post-surgery measures may be a better indicator of functional capacity and we have the ability to calculate the changes in these measures from Discharge to 4 wks post-surgery. We will assess QOL by questionnaire and activity by accelerometry as secondary outcomes to determine if NMES improves patient-reported QOL and free-living daily activity, respectively, vs. usual care. Covariates (eg, length of stay, time to start of CR, admission SPPB, etc) can be included in the models to control for potential confounders that might differ by group in the event that randomization fails to equate groups for these variables.

DRUG AND DEVICE INFORMATION

Drug (s) **Not applicable**

Device (s) **Not applicable**

The interventional device used in this study: EMPI Continuum complete electrotherapy system has received FDA approval (501K: K093324) for retarding disuse-related atrophy, which we believe is one of the primary mechanisms whereby CABG patients become more functional disabled in the early, post-surgical period. That is, muscle disuse secondary to pain, limited range of motion and muscle weakness causes skeletal muscle fiber atrophy and weakness, as well as mitochondrial rarefaction and dysfunction that further impair physical fitness.

Is it FDA approved:

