SUBJECT CHARACTERISTICS, IDENTIFICATION AND RECRUITMENT

Prior to our rationale for subject selection, we provide a brief accounting of inclusion/exclusion criteria. Ambulatory patients (50-80 yrs of age) scheduled for elective CABG and able to give informed consent will be recruited. Patients will be excluded if they have: 1) rheumatoid arthritis or other inflammatory/autoimmune diseases; 2) cancer, excluding non-melanoma skin cancer; 3) exercise-limiting peripheral vascular disease, neuromuscular disease or lower extremity neuromuscular dysfunction related to prior cerebrovascular event; 4) body mass index ≥ 38 kg/m² or 5) significant (moderate or greater) valvular heart disease that was not corrected surgically. We will also exclude patients with an existing lower blood clot or an implanted pacemaker or ICD, as both are contraindications for NMES (1). Patients will be excluded from further study post-operatively if they have serious complications that prolong hospitalization beyond 7 d post-surgery (eg, stroke, prolonged intubation, infection, etc), although this will likely be a small proportion of the population.

These criteria were chosen to obtain a cohort of CABG patients who are free of other clinical conditions that may complicate our ability to detect an effect of NMES on physical function (eg, cancer w/ its accompanying treatments or motor deficits due to CVA, etc) and who may have difficulty conducting the NMES (eg, very obese individuals may have difficulty obtaining muscle contractions with the NMES device because fat in their legs serves as an electrical insulator). Finally, we exclude those volunteers with contraindications for NMES use.

Literature cited:

1. Houghton, P. E., Nussbaum, E. L., and Hoens, A. M. (2010) Electophysical agents. Contraindications and precautions: an evidence-based approach to clinical decision making in physical therapy. *Physiother Can* **62**, 1-80

Number of Subjects:

We intend to enroll 48 volunteers. This will allow for n=36 to complete the study, conservatively assuming 25% total attrition rate: 15% dropout, 10% non-compliance, based on prior studies of NMES use in post-surgical populations (1) and compliance data in our prior training studies (85-95% compliance).

Literature cited:

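### Allocation is stratified by age and sex, but the analysis would normally leave both out; if either predicts the outcome change, reported intervals are too wide and the test is conservative

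*Combined protocol and SAP*

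**What the plan says.** The Study Design section under Methods and Procedures sets the allocation: "Patients will be randomized (1:1) to NMES or control intervention (n=18/group; Treatment Phase), with stratification for age and sex". It gives no age cut-points, number of strata or block size.

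The Statistical Analysis Plan gives the model: "A general linear mixed model will be used, with group and time as fixed effects". The contrast of interest is a change over time: "The primary comparison will be between measures at admission and 4 wks post-discharge". No group-by-time term is written out, although comparing changes between arms needs one.

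The same section has a covariate clause: "Covariates (eg, length of stay, time to start of CR, admission SPPB, etc) can be included in the models to control for potential confounders". It is permissive, its list of examples is open, and it names neither age nor sex. It is also conditional: covariates come in "in the event that randomization fails to equate groups for these variables". Age and sex are not named anywhere in the analysis plan.

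**The concern.** Stratified allocation makes the arms more alike on age and sex than simple randomisation would. An analysis that ignores those factors leaves their contribution in the residual variance, and so computes a standard error as if that balance had not been imposed. If the factors are prognostic, the reported standard error exceeds the real variability of the estimate.

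The covariate clause does not cure this, because its trigger is imbalance. The better stratification works, the less likely age and sex are to enter the model.

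At stake is efficiency. With about 36 completers, an interval wider than it need be makes a real effect easier to miss.

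**Working it through.** **The plan's own figure.** Number of Subjects says "We intend to enroll 48 volunteers" and "This will allow for n=36 to complete the study, conservatively assuming 25% total attrition rate: 15% dropout, 10% non-compliance". Check: 36 / (1 − 0.25) = 48, which agrees. The 36 itself cannot be reproduced, because the documents state no alpha, power, effect size or SD.

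**Inputs from the documents.** 1:1 allocation, 18 completers per arm, stratification by age and sex, model terms group and time, contrast on change to 4 weeks.

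**Assumptions.** Two-sided 5% test; results in units of the SD of the outcome change; R², the share of variance in that change explained by age and sex, from 0 to 0.30; in the simulation, 2×2 age-by-sex strata, permuted blocks of 4, and a true effect of 0.96 SD for power (chosen because it gives about 80% power at 18 per arm).

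**Formulas.** Unadjusted SE = √(2/18) = 0.333 SD. Adjusted SE = 0.333 × √(1 − R²). Ratio = 1/√(1 − R²). The 95% half-width uses t = 2.032 on 34 df unadjusted (2.032 × 0.333 = 0.677 SD) and t = 2.037 on 32 df adjusted. At R² = 0.20, for example, the ratio is 1/√0.80 = 1.118 and the adjusted half-width is 2.037 × 0.333 × √0.80 = 0.607 SD.

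**Results.** The last two columns come from 6,000 simulated trials of 36 patients per setting, using a linear model of the change score.

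| R² | SE too large by | Half-width, unadjusted → adjusted (SD) | Type I error, unadjusted / adjusted | Power at 0.96 SD, unadjusted / adjusted |
|---|---|---|---|---|
| 0 | 0% | 0.677 → 0.679 | 5.1% / 4.9% | 80.3% / 80.0% |
| 0.05 | 2.6% | 0.677 → 0.662 | 4.1% / 4.6% | not run |
| 0.10 | 5.4% | 0.677 → 0.644 | 4.4% / 5.4% | 79.6% / 82.7% |
| 0.20 | 11.8% | 0.677 → 0.607 | 3.0% / 4.7% | 81.4% / 86.9% |
| 0.30 | 19.5% | 0.677 → 0.568 | 2.4% / 4.9% | 82.9% / 91.0% |

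The Monte Carlo standard error of a 5% rate is √(0.05 × 0.95 / 6000) = 0.3 percentage points, so 4.1% and 4.4% do not differ meaningfully.

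**Where the loss sits.** At R² = 0.20 the actual spread of the estimate across simulated trials is 0.300 SD unadjusted and 0.298 SD adjusted. The mean reported SE is 0.333 and 0.298. The estimate is about as precise either way; the unadjusted analysis misreports that precision.

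**Which terms help.** In one simulated complete data set with three visits, the SE of the group-by-time contrast was 0.5737 without age and sex, 0.5737 with them as main effects, and 0.5445 with age-by-time and sex-by-time terms. A stable difference in level by age or sex cancels from a within-patient change. If the plan is read literally, with no group-by-time term, the arm contrast is the group main effect; main effects alone then reduced its SE from 0.629 to 0.547.

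**Attrition.** Further runs, with and without 25% attrition, gave intervals about 4–5%, 11–12% and 18–19% too wide at R² of 0.10, 0.20 and 0.30, with type I error of about 4–5%, 3.6% and 2–2.5%. The SE ratios do not depend on whether 18 or 24 per arm are analysed.

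**The case against.** The strongest objection is that the size of the effect is unknown and may be small. Nothing in the documents shows that age or sex predicts change in SPPB. The primary contrast already removes stable differences in level, so only effects on trajectory count, and eligibility narrows the age spread: "Ambulatory patients (50-80 yrs of age) scheduled for elective CABG and able to give informed consent will be recruited". With 48 randomised and a random 36 analysed, power at 0.96 SD was 80.5% unadjusted against 81.6% adjusted at R² = 0.05, and 80.7% against 82.7% at R² = 0.10. A clear gain needed R² of about 0.20 (81.4% against 87.1%). The study is also described as exploratory and proof of principle. All of this stands, and it is why the loss has to be stated conditionally.

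It is also fair that the plan does not forbid age and sex: the covariate list is open. What does not stand is that this settles the matter, since entry depends on an imbalance that stratification is there to prevent.

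A reader might go further and infer that omitting the factors invalidates the test or inflates false positives. It does neither: the error is on the conservative side and the estimate is not biased. Nor is the benefit of stratification thrown away, since the allocation has already secured nearly all of the true precision.

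**Conclusion.** The mismatch between design and analysis is on the page: age and sex shape the allocation, and the analysis rule would normally leave them out. Its consequence is conditional. For an assumed R² of 0.05 to 0.30, the reported standard error is about 3% to 19.5% too large, the 95% interval about 2% to 19% too wide, and a 5% test runs at about 2% to 4.5%. At R² of zero there is no loss.

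These figures rest on the assumed prognostic strength, strata and block size, and on a linear model of change standing in for the mixed model, whose arm contrast the plan does not write out. In a model that already adjusts for baseline, read R² as the share of the remaining variance.

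This is an efficiency point of minor to moderate weight, not a validity error. It is worth acting on because the cost is small: if age and sex predict nothing, the two-term model widens the interval by at most about 1%.

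**What to change.** In the Statistical Analysis Plan, pre-specify age and sex in every between-arm model, whatever the observed balance. Use age as grouped for allocation (stating the groups) or as continuous. By outcome:

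- **SPPB and SF-36:** either model the 4-week value adjusted for the pre-surgery value, age and sex; or keep the mixed model, write out the group-by-time contrast, and add age-by-time and sex-by-time terms.
- **6-minute walk:** first reconcile Study Design, whose opening sentence includes this test before surgery, with the Physiological Testing heading under Procedures, which excludes it. If there is no pre-surgery value, adjust for the discharge value, age and sex.
- **Accelerometry:** the device is issued at discharge, so there is no pre-surgery value. Enter age and sex as main effects.

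The cost is a few sentences in the plan and no new data, since age and sex are known at randomisation. The adjusted model of the 4-week value spends about two extra degrees of freedom on age and sex. The mixed-model option with three visits adds about six parameters (two main effects and four interactions), which makes the first option the leaner one at 36 completers.

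### The Study Design section ends treatment 4 weeks after surgery, but the NMES course and the SAP's primary end point count 4 weeks from discharge, so the stop date and the final test each have two dates

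*Combined protocol and SAP*

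**What the plan says.** Two anchors are used for the end of the study period.

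**Counted from surgery**
- Study Design, Treatment Phase: patients "will continue in this Treatment phase until 4 weeks post-CABG surgery".
- Study Design, last visit: "4 wk Post-surgery testing will be identical to Discharge testing".
- Summary: after the pre-surgery test, evaluations come "upon discharge and 4 weeks Post-CABG surgery".
- Questionnaires: the SF-36 is scheduled under the same post-surgery visit label.
- Statistical Analysis Plan: the alternative change score runs from Discharge to 4 weeks after surgery.

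**Counted from discharge**
- Summary: the home programme is described as "continuing for 4 weeks following discharge from the hospital".
- Procedures, NMES paragraph: home sessions start at discharge, 5 days a week, 45 minutes each, for 4 weeks.
- Statistical Analysis Plan: both the stated goal and the primary comparison end 4 weeks after discharge. Their starting point is admission.

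**Bearing on the same dates**
- Study Design also places the last test after the course is finished: "Following completion of the 4 wk intervention".
- The Summary gives the phase a fixed length: "accelerometry will be used to monitor weight-bearing physical activity during the 4 week treatment phase". The accelerometer for that phase is handed out at Discharge testing: "At this time, volunteers will receive an accelerometer, which will be worn during three (3) 5-day periods during the Treatment phase".

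No visit window is given, and no rule says which anchor prevails.

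**The concern.** A 4-week course that begins at discharge cannot be complete 4 weeks after an operation that came before discharge. Staff working from the Treatment Phase sentence would stop stimulation early, and the number of sessions would fall as length of stay rises. Staff working from the NMES paragraph and the analysis plan would test later than the visit label says. Nothing prevents the two rules from being applied to different patients.

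Two quantities are at stake. One is the planned dose: the NMES paragraph treats an effective stimulus as essential at this stage and leaves dose reduction to later studies. The same section tracks compliance, and a patient who did everything asked up to day 28 after a 7-day stay would still have completed only three quarters of the course. The other is the day of the primary Short Physical Performance Battery (SPPB) measurement, taken while patients are still recovering from surgery.

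**Working it through.** **The plan's own figure.** The only derived sample-size number is enrolment: 36 / (1 − 0.25) = 48, which matches Number of Subjects. It does not depend on the visit date, so this point leaves it untouched.

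**Inputs**
- Surgery is day 0; discharge is day L.
- Course: 4 weeks × 5 sessions = 20 home sessions; 20 × 45 = 900 minutes (Procedures, NMES paragraph).
- L = 7: the limit in the rule that removes patients whose serious complications keep them in hospital beyond 7 days (Subject Characteristics; Inclusion/Exclusion Criteria).
- L = 4: an assumption. The documents give no length-of-stay distribution.

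**Formulas**
- End date counted from surgery: day 28. Counted from discharge: day 28 + L. Gap = L.
- Home days available if treatment stops at day 28: 28 − L.
- Expected home sessions: 5 × (28 − L) / 7. Minutes: sessions × 45.

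| Discharge day L | Home days to day 28 | Expected sessions (of 20) | Minutes (of 900) | Final test if counted from discharge |
|---|---|---|---|---|
| 4 (assumed) | 24 | 17.1 (86%) | 771 | day 32 |
| 5 | 23 | 16.4 (82%) | 739 | day 33 |
| 6 | 22 | 15.7 (79%) | 707 | day 34 |
| 7 | 21 | 15.0 (75%) | 675 | day 35 |

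In whole sessions, three full weeks give 15. The remaining 3, 2, 1 or 0 days add 1–3, 0–2, 0–1 or 0, depending on where the two rest days fall. That gives 16–18, 15–17, 15–16 and 15 sessions for L = 4, 5, 6 and 7.

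**What does not change.** The in-hospital familiarisation sessions of about 15 minutes happen under either date, so they do not alter the gap. The accelerometer periods need 3 × 5 = 15 days and fit within 21 to 28 days.

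**Position against cardiac rehabilitation (CR).** The Summary has CR starting 4 to 6 weeks after surgery, that is day 28 to 42. A final test on day 32 to 35 lies inside that span. The Purpose section instead counts about 4 to 6 weeks from discharge, which for L = 4 to 7 begins on day 32 to 35, the same days as the test.

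**The case against.** The strongest reply is that this is loose shorthand. Only one sentence, in the Treatment Phase paragraph, actually ends treatment at day 28. The Summary dates only the evaluation from surgery and runs the programme itself from discharge; the Questionnaires section merely repeats a visit label. The NMES paragraph, which is the dosing instruction, is explicit, and staff delivering NMES would most naturally follow it. The analysis plan uses both phrasings for what can only be one visit. On this view the shortfall of about 3 to 5 sessions is conditional on staff choosing the less natural text, and no effect on SPPB has been shown.

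Much of that stands. The dose conflict is confined to the one sentence, and the documents do not show that staff would follow it. It remains an operational stop rule that contradicts the dosing text, and the visit date is stated both ways in several places.

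Three further points are fair:
- A week is not a hard ceiling. The 7-day rule covers serious complications only; a longer stay for another reason would widen the gap.
- The surgery anchor has some support: on the Summary's CR timing, a day-28 test comes at or before usual CR entry, which suits an aim framed as the period before CR.
- The NMES paragraph gives 4 weeks as an approximate average time to CR at the centre, so some patients will enter earlier.

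A reader might also infer that the primary analysis has no identifiable time point. It does: only one assessment follows Discharge testing, so the visit is clear and only its calendar day is in doubt.

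**Conclusion.** The conflict is real, lies in the current text, and should be corrected. The end of treatment and the final test each carry two dates that differ by the post-operative stay: 7 days for a day-7 discharge, 4 days for an assumed day-4 discharge. Following the Treatment Phase sentence would leave about 15 to 17 of 20 home sessions; following discharge puts the final test on about day 32 to 35.

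Discharge is the likelier intended anchor. The dosing paragraph and the primary comparison already use it, and the Objectives justify the SPPB as "a metric whose change in the first month post-hospitalization has been shown to predict re-hospitalization and death".

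It would be tempting to conclude that the ambiguity biases the treatment comparison. The documents do not support that: the timing applies to both arms, the same visit enters the model, and no differential effect is shown. The size figures rest on an assumed day-4 discharge at one end and on the complication rule at the other.

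**What to change.** Use discharge as the single anchor.

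- In Study Design, end the Treatment Phase 4 weeks after discharge.
- In the Summary, Study Design and Questionnaires sections, date and label the final visit as 4 weeks after discharge.
- In the Statistical Analysis Plan, change the Discharge-based change score to end at the same visit.
- State one visit window, identical in both arms. Its width is the sponsor's choice.
- Schedule the final test before the first CR session where possible, and record the dates of both.

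**Cost.** These are wording changes with no extra visits. Some final tests move by 4 to 7 days against the post-surgery schedule for stays of that length. Time since surgery at the final test then varies with length of stay: a 3-day spread (day 32 to 35) for stays of 4 to 7 days, plus the visit window. On the Summary's CR timing, a later test may fall after CR entry for some patients, which sits less well with the aim. The analysis plan already allows length of stay and time to start of CR as covariates, so both can be examined with the recorded dates.
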